7.3 Final Analysis

The objective of the final analysis is to provide an update on safety and tolerability, and efficacy results. The statistical methods used in the final analysis will be the same as those employed in the primary analysis. The final analysis will be based on subject data collected through study discontinuation or at the end of the study which includes the 30 days safety follow-up, whichever occurs first. **At that time the database will be cleaned, processed and a locked database will be used in the analysis.**

8. Data Screening and Acceptance

8.1 General Principles

The objective of the data screening is to assess the quantity, quality, and statistical characteristics of the data relative to the requirements of the planned analyses.

8.2 Data Handling and Electronic Transfer of Data

The Amgen Global Study Operations-Data Management (GSO-DM) department will provide all data to be used in the planned analyses. This study will use the RAVE database.

8.3 Handling of Missing and Incomplete Data

The following imputation for missing or incomplete data will be performed if required:

Incomplete adverse event and concomitant medication dates missing data will be imputed as described in [Appendix A](#). If imputed dates are used, then they will be identified as such in the final study report.

Laboratory measurements that are below the quantification limits will be considered equal to the lower limit of quantification for all analyses unless explicitly noted otherwise.

Non-pharmacokinetic measurements (eg, ██████ data) that are below the lower limit of quantification will be considered equal to half of the lower limit of quantification for all analyses unless specified otherwise.

PK concentrations that are below the quantification limits will be set to zero when engaging non-compartmental model to compute PK parameters.

8.4 Detection of Bias

Lack of protocol compliance and the potential for biased statistical analyses will be examined by assessing the incidence of important protocol deviations in each cohort. The clinical study team will identify and document the criteria for important protocol deviations.

8.5 Outliers

Pharmacokinetic (PK) concentration data will be evaluated for outliers by visual inspection, and decisions to re-assay individual samples will be made in accordance with standard pharmacokinetic evaluation practice.

8.6 Distributional Characteristics

Where appropriate, the assumptions underlying the proposed statistical methodologies will be assessed. If required, data transformations or alternative non-parametric methods of analyses will be utilized.

8.7 Validation of Statistical Analyses

Programs will be developed and maintained, and output will be verified in accordance with current risk-based quality control procedures.

Tables, figures, and listings will be produced with validated standard macro programs where standard macros can produce the specified outputs.

The production environment for statistical analyses consists of Amgen-supported versions of statistical analysis software; for example, the SAS System version 9.4 or later.

9. Statistical Methods of Analysis

9.1 General Considerations

All analyses for the study are [REDACTED] and hypothesis generating. Descriptive statistics will be used to summarize most analysis results.

Data analysis will occur at the following time points:

- The primary analysis will occur when target enrollment is complete and each subject either completes 2 months on study or withdraws from the study.
- A final analysis is planned when the last subject is assessed or receives an intervention for evaluation in the study.

9.2 Subject Accountability

A summary of subject disposition with discontinuation reasons, and oprozomib completion and discontinuation will be provided. Key study dates for the first subject enrolled, last subject enrolled, and last subject's end of study will be presented **for non-roll over subjects and roll-over subjects.**

A subject listing and summary noting inclusion in each analysis subset will be provided for all subjects enrolled. A subject listing noting duration of oprozomib administration, reason for discontinuation of treatment, and reason for discontinuing the study will be provided. A list of subjects screened but not enrolled (screen failures) will be provided.

9.3 Important Protocol Deviations

Important Protocol Deviations (IPDs) categories are defined by the study team before the first subject's initial visit and updated during the IPD reviews throughout the study prior to database lock. These definitions of IPD categories, subcategory codes, and descriptions will be used during the course of the study. Eligibility deviations are defined in the protocol.

9.4 Demographic and Baseline Characteristics

9.4.1 Demographics

Demographic (ie, age, age groups [18-64, 65-74, 75-84 and > = 85], sex, race, ethnicity) and baseline characteristics will be summarized by dose cohort and overall using

descriptive statistics. If multiple races have been reported for a subject, the subject will be categorized as multiple race as well as by the combination of race.

9.4.2 Medical History

The number (%) of subjects who experienced a prior disease or disorder will be summarized by system organ class and preferred term for non-roll over subjects and roll-over subjects.

9.4.3 Baseline Characteristics

The following baseline characteristics will be summarized for non-roll over subjects:

- **ECOG performance Status**
- **Disease stage**
- **Myeloma light chain**
 - **Kappa light chain**
 - **Lambda light chain**
- **Myeloma immunoglobulin**
 - **Immunoglobulin A**
 - **Immunoglobulin D**
 - **Immunoglobulin E**
 - **Immunoglobulin G**
 - **Immunoglobulin M**
- **Pathology (FISH)**
 - **t(11;14)**
 - **del(13q;14)**
 - **t(4;14)**
 - **t(14;16)**
 - **Chromosome 1 abnormalities (ie, 1q21 amplification, 1p deletion)**
 - **Chromosome 13 abnormalities (ie, chromosome 13 deletion)**
 - **Hyperdiploid**
 - **Non-hyperdiploid**
- **Prior lines of therapy**
- **Prior radiotherapy**
- **Exposure and refractory status to**
 - **Bortezomib**
 - **Carfilzomib**
 - **Lenalidomide**
 - **Pomalidomide**
 - **Anti-CD38 antibody (including Daratumumab)**
- **Prior transplant**

9.5 Efficacy Analyses

All efficacy assessments will follow IMWG uniform response criteria and be performed every 4 weeks (\pm 1 week). See [Section 9.5.2](#) for details.

9.5.1 Analyses of Primary Efficacy Endpoint(s)

NA

9.5.2 Analyses of Secondary Efficacy Endpoint(s)

Overall response rate (defined as the proportion of best overall response of stringent complete response [sCR], complete response [CR], very good partial response [VGPR], and partial response [PR]), best overall response, PFS (defined as the number of months from subject's first study dose date to the earlier of disease progression or death due to any cause), and DOR will be summarized for all subjects overall, by formulation, by dose cohort level, and by formulation and dose cohort level along with 95% confidence intervals when applicable.

All subjects who receive treatment with any amount of the OPomd and have a baseline disease assessment and at least 1 post-baseline disease assessment will be included in the efficacy analyses. Additional efficacy analyses will be performed based on subjects who receive treatment with any amount of OPomd.

9.6 Safety Analyses

9.6.1 Analyses of Primary Safety Endpoint(s)

Subject incidence of all treatment emergent adverse events of interest will be tabulated by system organ class and preferred term. Tables of fatal adverse events, serious adverse events, adverse events leading to withdrawal from investigational product, other protocol-required therapies or from study, and adverse events of interest will also be provided. Relevant laboratory and vital sign (temperature, heart rate, respiratory rate, and blood pressure) data will be displayed by visit and time (when available), with CTCAE (Version 4.03) Grade 3 and 4 values identified where appropriate. Additionally, all laboratory data will be summarized by CTCAE Grade.

ECG analyses include summary changes from baseline for ECG intervals, summaries of the proportion of subjects with on-study corrected QT interval (QTc) values that reach certain values (eg, $>$ 450 msec), and summaries of the proportion of subjects with categorical changes from baseline (eg, $<$ 30 msec).

9.6.2 Adverse Events and Disease-related Events

The number of DLTs and adverse events at each dose level will be summarized separately for each oprozomib formulation in combination with dexamethasone and in combination with pomalidomide and dexamethasone.

The Medical Dictionary for Regulatory Activities (MedDRA) version 19.0 or later will be used to code all events categorized as adverse events to a system organ class and a preferred term.

The subject incidence of adverse events will be summarized for all treatment-emergent adverse events, serious adverse events, adverse events leading to withdrawal of investigational product, and fatal adverse events and adverse events of interest when defined.

Subject incidence of all treatment-emergent adverse events, serious adverse events, adverse events leading to withdrawal of investigational product, and fatal adverse events will be tabulated by system organ class and preferred term in alphabetical order.

Subject incidence of events of interest (standardized MedDRA queries and/or Amgen customized queries) will also be summarized according to their categories and preferred term.

In addition, summaries of treatment-emergent and serious adverse events by preferred term in any treatment arm will be provided in descending order of frequency.

Summaries of treatment-emergent and serious adverse events will be tabulated by system organ class, preferred term, and grade.

Subject incidence of disease-related events will be summarized for all treatment-emergent disease-related events and fatal disease-related events.

Roll-over subjects: Subject incidence treatment-emergent adverse events and treatment-emergent serious adverse events will be tabulated by system organ class, preferred term, grade and preferred term in descending order of frequency.

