## 5. BACKGROUND AND RATIONALE

### 5.1 Multiple Myeloma Background

Multiple myeloma is a neoplastic plasma-cell disorder that is characterized by clonal proliferation of malignant plasma cells in the bone marrow microenvironment, monoclonal protein in the blood or urine and associated organ dysfunction (Palumbo and Anderson, 2011). Multiple myeloma accounts for almost 2% of all cancers and 20% of hematologic malignancies. The disease is slightly more common in males and African Americans (Siegel, 2015). Multiple myeloma remains an incurable cancer, although recent improved understanding of pathogenesis of myeloma has led to the development of new treatments and improved survival (Smith and Yong, 2013).

Myeloma arises from an asymptomatic premalignant proliferation of monoclonal plasma cells that are derived from post-germinal center B cells. Multistep genetic and micro-environmental changes lead to the transformation of these cells into a malignant neoplasm. Myeloma is thought to evolve most commonly from a monoclonal gammopathy of undetermined clinical significance (MGUS) that progresses to smoldering myeloma and ultimately to symptomatic myeloma.

The uncontrolled growth of myeloma cells has many consequences, including skeletal destruction, bone marrow failure, increased plasma volume and viscosity, suppression of normal immunoglobulin production, and renal insufficiency (Durie, 2011).

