### 5.3 Risk Assessment

Important identified risks to human subjects with the use of oprozomib include diarrhea, nausea, vomiting, abdominal pain, GI hemorrhage, constipation, fatigue, hypophosphatemia, dehydration, tumor lysis syndrome, decreased appetite, anemia, thrombocytopenia, infection (pneumonia, sepsis, and urinary tract infection), hypotension, acute renal failure and syncope (the last three only secondary to diarrhea and dehydration).

Please refer to Section 7 of the Oprozomib IB for a description of important potential risks, which include posterior reversible encephalopathy syndrome (PRES).

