## **12. SAFETY DATA COLLECTION, RECORDING, AND REPORTING**

### **12.1 Definition of Safety Events**

#### **12.1.1 Disease-Related Events**

Disease-Related Events are events (serious or non-serious) anticipated to occur in the study population due to the underlying disease.

Disease-Related Events that do not qualify as Adverse Events or Serious Adverse Events:

- An event which is part of the normal course of multiple myeloma (eg, disease progression in oncology or hospitalization due to disease progression)
- Death due to the disease under study (multiple myeloma)

Disease-Related Events that would qualify as an Adverse Event or Serious Adverse Event:

- An event based on the underlying disease that is worse than expected as assessed by the investigator for the subject's condition, or if the investigator believes there is a causal relationship between the study treatment and disease worsening, this must be reported as an Adverse Event or Serious Adverse Event (and not as a Disease-Related Event)

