### 12.1.3        **Serious Adverse Events**

A serious adverse event is defined as an adverse event that meets at least 1 of the following serious criteria (unless it meets the definition of a Disease-Related Event as defined in Section 12.1.1):

- fatal
- life threatening (places the subject at immediate risk of death)
- requires in patient hospitalization or prolongation of existing hospitalization
- results in persistent or significant disability/incapacity
- results in a congenital anomaly/birth defect
- other medically important serious event

An adverse event would meet the criterion of “requires hospitalization”, if the event necessitated an admission to a health care facility (eg, overnight stay).

If an investigator considers an event to be clinically important, but it does not meet any of the serious criteria, the event could be classified as a serious adverse event under the criterion of “other medically important serious event”. Examples of such events could include allergic bronchospasm, convulsions, blood dyscrasias, drug induced liver injury (DILI) (see [Appendix A](#) for DILI reporting criteria), or events that necessitate an emergency room visit, outpatient surgery, or urgent intervention.

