It is defined as the first day that protocol specified study treatment is administered to the subject.

Study Day

Post study day: study day= (date - date of Study Day 1) + 1

Pre study day: study day= (date – date of Study Day 1)

Time to Response (TTR)

Time to response defined as the interval from the first administration of study treatment to the first documentation of confirmed response. Response is defined as any of the following: stringent complete response (sCR), complete response (CR), very good partial response (VGPR), or partial response (PR) (all according to Revised International Myeloma Working Group Uniform Response Criteria [IMWG-URC]).

Time to response is calculated as the number of days:

(date of first response – date of study day 1 +1).

Time to response will be calculated only for subjects with response.

Treatment-Emergent Adverse Event (TEAE)

Treatment-emergent adverse events are events categorized as Adverse Events (AEs) **starting on or after first dose of investigational product as determined by the flag indicating if the adverse event started prior to the first dose on the Events CRF and up to and including 30 days after the last dose of investigational product or the End of Study date, whichever is earlier.**

Treatment-Related AE

A treatment-related AE is any treatment-emergent AE that per investigator review has a reasonable possibility of being caused by study treatment.

Disease-Related Events

Disease-Related Events are events (serious or non-serious) anticipated to occur in the study population due to the underlying disease.

C_{max}

Maximum observed serum concentration.

t_{max}

Time to C_{max}

AUC_{last}

Area under the concentration-time curve from time 0 (time of investigational product administration) to the time of the last quantifiable concentration.

Progression free survival

The number of months from subject's first study dose date to the earlier of disease progression or death due to any cause.

Progression free survival data will be censored as described below:

- **Patients who are alive and do not have documented disease progression at the time of analysis will be censored at the date of the last disease assessment.**
- **Patients who are alive and do not have disease assessment at the time of analysis will be censored at the first study dose date.**

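### The SAP plans no table showing what the disease-related events were; the gap matters mainly for infection and is cheap to close

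*SAP*

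**What the plan says.** Protocol 12.1.1 defines a class headed "Disease-Related Events that do not qualify as Adverse Events or Serious Adverse Events". It covers events in the normal course of myeloma and death from myeloma. The same section sends an event back to AE or SAE status if the investigator finds it worse than expected for that subject or believes study treatment contributed. Protocol 12.1.3 applies the SAE criteria to an event "unless it meets the definition of a Disease-Related Event as defined in Section 12.1.1". SAP Section 5 restricts treatment-emergent AEs to events placed in the AE category.

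SAP 9.6.2 then treats the two classes differently:

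- **AEs.** MedDRA "will be used to code all events categorized as adverse events to a system organ class and a preferred term". "Summaries of treatment-emergent and serious adverse events will be tabulated by system organ class, preferred term, and grade".
- **DREs.** "Subject incidence of disease-related events will be summarized for all treatment-emergent disease-related events and fatal disease-related events". No coding, system organ class, preferred term or grade is mentioned.

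Protocol 5.3 lists among the identified risks of oprozomib "anemia, thrombocytopenia, infection (pneumonia, sepsis, and urinary tract infection), hypotension, acute renal failure". It adds that hypotension, acute renal failure and syncope arise only through diarrhea and dehydration. Protocol 5.1 lists among the consequences of myeloma "bone marrow failure, increased plasma volume and viscosity, suppression of normal immunoglobulin production, and renal insufficiency".

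**The concern.** An event type that is both an identified drug risk and a complication of the disease can be filed under either label. Once it is filed as a DRE, it leaves the treatment-emergent AE tables, the SAE tables and the primary safety endpoint (incidence of treatment-related, treatment-emergent AEs). It reappears only inside a count that does not name it.

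The study is open-label, non-randomized and has no control arm, so no background rate exists against which to check the labels. Formulation and dose are to be chosen from all escalation-cohort data (Protocol 13.3.2, SAP 7.2), and those cohorts hold 4 to 10 OPomd subjects each. A few infections labelled differently in two cohorts could change how the cohorts compare, and a reader of the planned output could not see that this had happened.

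**Working it through.** **1. Which overlapping risks have another route into the report?**

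- *Anemia and thrombocytopenia.* SAP 9.6.1 and 9.6.3 summarize laboratory data by CTCAE grade, with worst post-dose grade, grade shifts and a Grade 3 or higher listing. None of this depends on the AE or DRE label. Hemoglobin, platelets and ANC are on the analyte list. The laboratory picture is covered.
- *Renal failure.* Creatinine is on the same list. The restriction in Protocol 5.3 to diarrhea and dehydration also narrows the overlap with myeloma kidney disease.
- *Infection (pneumonia, sepsis, urinary tract infection).* No laboratory table stands in for these. If labelled as DREs, they are identified in no planned table.

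**2. Reproducing Table 2 (safety analysis set, N = 52).** Subjects with any treatment-emergent DRE:

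- ODex: 1 + 1 = 2 of 13
- OPomd, in table order: 0 + 0 + 1 + 2 + 0 + 1 = 4 of 39
- Total: 2 + 4 = 6; 6/52 = 11.5% (exact 95% CI 4.4 to 23.4)
- Grade 2 or higher: 4/52 = 7.7%. Grade 3 or higher: 3/52 = 5.8% (1.2 to 15.9). Grade 4 or higher, serious, and fatal: 1/52 = 1.9% each

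All agree with the printed figures. Within OPomd, both subjects with a Grade 3 or higher DRE are in GR 200 mg: 2/5, against 0/34 in the other cohorts (39 − 5 = 34). The only serious and the only fatal DRE are also there.

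**3. How far could pooling move the totals?** Table 2 does not say whether a subject with a DRE also had an AE of that grade, so only bounds are possible. For cohort c with N_c subjects:

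- lower bound = sum over c of max(AE_c, DRE_c)
- upper bound = sum over c of min(AE_c + DRE_c, N_c)

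For Grade 3 or higher, in table order, AE counts are 3, 7, 4, 4, 8, 5, 8, 6 (sum 45). DRE counts are 1, 0, 0, 0, 0, 2, 0, 0. GR 200 mg is already 5/5 and cannot rise, so the upper bound is 4 + 7 + 4 + 4 + 8 + 5 + 8 + 6 = 46.

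| Row | AE alone | AE + DRE, overall | GR 200 mg, AE alone | GR 200 mg, AE + DRE |
|---|---|---|---|---|
| Grade ≥ 3 | 45/52 (86.5%) | 45 to 46 (86.5% to 88.5%) | 5/5 | 5/5 |
| Grade ≥ 4 | 13/52 (25.0%) | 13 to 14 (25.0% to 26.9%) | 4/5 | 4/5 to 5/5 |
| Serious | 27/52 (51.9%) | 27 to 28 (51.9% to 53.8%) | 4/5 | 4/5 to 5/5 |
| Fatal | 1/52 (1.9%) | 1 to 2 (1.9% to 3.8%) | 1/5 | 1/5 to 2/5 |

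The fatal row reaches 2/5 only if the fatal AE and the fatal DRE belong to different subjects, which the documents do not state.

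**4. What cannot be computed.** Incidence by event type, infection included, cannot be pooled, because no preferred terms are given for the DREs.

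**The case against.** The case against has several strong parts.

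- *Grade is reported.* A reader might infer from the SAP sentence that DREs are not reported by severity. Table 2 shows otherwise: by cohort, it gives Grade 2, 3 and 4 or higher, serious, leading to discontinuation, and fatal. This stands. The SAP does not promise those rows, but they were produced, so the real gap is event type.
- *No hidden harm is shown.* A reader might also infer that part of oprozomib's toxicity has been moved out of the AE tables. The documents do not support that. No DRE is identified as an infection, cytopenia or renal event, and the protocol's own examples are progression, hospitalization for progression and death from myeloma. The 6/52 and 2/5 counts show how often the label was used, not how often it was misused.
- *Overlapping events were captured as toxicity.* Table 1 records acute kidney injury, febrile neutropenia, decreased neutrophil count and thrombocytopenia as DLTs. This stands as evidence that investigators did not routinely ascribe such events to disease.
- *The safeguard in Protocol 12.1.1.* Events suspected to be causal or worse than expected must be AEs. This limits any leak to misattributed events, but it rests on the same unaided judgement, so it does not settle the question.
- *Decisions rest on more than AE tables.* The MTD is based on DLTs, and the dose level review team sees all available data. This is true and keeps the severity low. Formulation and dose selection still draw on the wider safety summaries.

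**Conclusion.** The concern holds in a narrow form. As written, SAP 9.6.2 produces no table saying what the treatment-emergent DREs were and promises no grade breakdown, although Table 2 supplies one. The consequence is confined mainly to infection, the one overlapping risk without a laboratory counterpart.

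The effect on overall totals is small: at most one more subject in each of the Grade 3 or higher, Grade 4 or higher, serious and fatal rows. It is larger within one small cohort, GR 200 mg, where fatal incidence is 1/5 or 2/5 depending on whether the two fatal entries are the same subject.

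This rests on Table 2 as printed and on bounds that assume nothing about subject overlap. Misattribution is possible but not shown, and without event types the planned output could neither confirm it nor rule it out. Minor severity.

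**What to change.** In SAP 9.6.2:

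1. Extend the MedDRA coding statement to events categorized as disease-related.
2. Tabulate treatment-emergent DREs by system organ class, preferred term and worst grade, by formulation and dose level. Write the grade, seriousness and fatal rows already shown in Table 2 into the plan.
3. Add one supportive table pooling AEs and DREs for the identified risks that overlap with myeloma (chiefly infection, also anemia and thrombocytopenia), by formulation and dose level and regardless of the investigator's category. Count each subject once.

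The cost is coding the DREs and programming two tables. AEs and DREs are already collected on the same Event CRF (Protocol 12.2.1 and 12.2.2.1), so no new data are needed and no clinical rule changes. The final analysis is planned with the same methods as the primary analysis, so the tables can be added there. The downside is that the pooled table will include some true disease events, so it should be labelled supportive and read beside the AE tables, not in place of them.
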